#### **8.2.10. Headache Pain Recurrence Postdose**

The proportion of subjects who have pain recurrence between 2 to 24 hours postdose during each DB treatment period will be summarized by treatment group for the FAS1 and FAS2. Pain recurrence between 2 to 24 hours is defined as pain-free at 2 hours postdose, with pain (mild, moderate, or severe) reported at 24 hours postdose. The corresponding p-values from Fisher's exact test will be computed for the comparison between treatment groups.

#### **8.2.11. Sustained Headache Pain Relief Postdose**

The proportion of subjects who have sustained pain relief at 2 to 24 hours postdose during each DB treatment period will be summarized by treatment group for the FAS1 and FAS2. Sustained pain relief at 2 to 24 hours is defined as pain relief at 2 hours

postdose, with no use of rescue medication and no worsening of headache pain within 2 to 24 hours postdose. The corresponding p-values from Fisher's exact test will be computed for the comparison between treatment groups.

#### **8.2.12. Sustained Headache Pain Freedom Postdose**

The proportion of subjects who have sustained pain freedom at 2 to 24 hours postdose during each DB treatment period will be summarized by treatment group for the FAS1 and FAS2. Sustained pain freedom at 2 to 24 hours is defined as pain-free at 2 hours postdose, with no use of rescue medication and no recurrence of headache pain within 2 to 24 hours postdose. The corresponding p-values from Fisher's exact test will be computed for the comparison between treatment groups.

#### **8.2.13. Use of Rescue Medication Postdose**

The proportion of subjects who use rescue medication at 2 to 24 hours postdose during each DB treatment period will be summarized by treatment group for the FAS1 and FAS2. The corresponding p-values from Fisher's exact test will be computed for the comparison between treatment groups.

#### **8.2.14. Subject-Rated Treatment Satisfaction Postdose**

The possible values of the subject treatment satisfaction scale are: 1 = very satisfied; 2 = satisfied; 3 = somewhat satisfied; 4 = neither satisfied nor dissatisfied; 5 = somewhat dissatisfied; 6 = dissatisfied; 7 = very dissatisfied.

Subject-rated treatment satisfaction based on a 7-point scale at 2 and 4 hours postdose during each DB treatment period will be summarized by treatment group for the FAS1 and FAS2. The corresponding p-values from the Wilcoxon rank-sum test will be computed for the comparison between treatment groups.

The subject-rated treatment satisfaction score at 2 and 4 hours postdose and the baseline PPMQ-R response for the same question will be compared for the DFN-15 group only. The corresponding p-value from the Wilcoxon rank-sum test will be computed for this comparison.

The difference between the subject-rated treatment satisfaction score at 2 and 4 hours postdose and the baseline PPMQ-R response for the same question will be summarized by treatment group for the FAS1 and FAS2. P-values from the Wilcoxon rank-sum test will be computed for the comparison between overall treatment satisfaction score at 2 and 4 hours postdose and baseline PPMQ-R response for the DFN-15 group only. P-values from the Wilcoxon signed-rank test will be computed for the difference between baseline PPMQ-R and post baseline for DFN-15 group only.

Additionally, the subject-rated treatment satisfaction scores at 2 and 4 hours postdose will be categorized to report "satisfied" versus "neither/dissatisfied";

“satisfied/neither” versus “dissatisfied”; and “satisfied” versus “neither”, and “dissatisfied”. The “satisfied” category consists of scores 1-3, and the “neither/dissatisfied” category consists of scores 4-7. The “satisfied/neither” group consists of scores 1-4, and the “dissatisfied” group consists of scores 5-7. The “neither” group consists of the score 4. Proportions of subjects in the “satisfied” versus “neither/dissatisfied”, the “satisfied/neither” versus “dissatisfied”, and the “satisfied” versus the “neither” and “dissatisfied” categories will be summarized by treatment group for the FAS1 and FAS2. The corresponding p-values from Fisher’s exact test will be computed for the comparison between treatment groups.

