**Table 9-2 eDiary Assessments**

Assessment/Time	Baseline	DB1 and DB2 Treatment Period					
		Predose	Postdose				
			15, 30, 45 min	1 h and 1.5 h	2 h and 4 h	24 h	
Migraine date/time and aura information, study drug, last food intake and fat content, and rescue medication taken for migraine attacks			As applicable 				
Time to meaningful pain relief (based on subject's perception)			As applicable up to 2 h postdose				
Time to pain freedom			As applicable up to 2 h postdose				
Pain level		X	X	X	X	X	
Functional disability		X			X	X	
Presence of nausea/photophobia/phonophobia/and cutaneous allodynia		X	X	X	X	X	
Most bothersome symptom (selected between nausea, photophobia and phonophobia) 		X					
PPMQ-R	X					X	
Subject treatment satisfaction					X 		

Abbreviations: h = hour(s); min = minutes; PPMQ-R = Patient Perception of Migraine Questionnaire-Revised

 End of migraine pain may occur more than 24 hours postdose.

 The most bothersome symptom will be collected only if more than 1 symptom is present predose; if only 1 symptom is present, it will be considered the most bothersome.

 Treatment satisfaction baseline for the migraine medication to be collected before randomization in the PPMQ-R.

CONFIDENTIAL

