- The proportion of subjects who have sustained pain freedom at 2 to 24 hours postdose (i.e., pain-free at 2 hours postdose, with no use of rescue medication, and no recurrence of headache pain within 2 to 24 hours postdose) compared between DFN-15 and placebo.
- The proportion of subjects who use rescue medication after 2 hours (2 to 24 hours) postdose compared between DFN-15 and placebo.
- Treatment satisfaction at 2 hours and 4 hours postdose as determined on a 7-point scale compared between DFN-15 and placebo. DFN-15 will also be compared to same question in the Baseline PPMQ-R.
- Treatment satisfaction as measured by PPMQ-R at 24 hours postdose compared between DFN-15 and placebo.

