#### **8.2.7. Change in Functional Disability Score Postdose**

The values of the functional disability scale are: 0 = no disability, able to function normally; 1 = performance of daily activities mildly impaired, can still do everything but with difficulty; 2 = performance of daily activities moderately impaired, unable to do some things; 3 = performance of daily activities severely impaired, cannot do all or most things, bed rest may be necessary.

The change in functional disability score from baseline to 2, 4, and 24 hours postdose during each DB treatment period will be summarized by treatment group for the FAS1 and FAS2. The corresponding p-values from the Wilcoxon rank-sum test will be computed for the comparison between treatment groups. P-values from the Wilcoxon signed-rank test will be computed for the change from baseline within each treatment group.

The following levels of change from baseline in functional disability score will be compared between DFN-15 and placebo in each DB period: 3 point change, 2 point change, 1 point change, 0 point change, -1 point change, -2 point change, and -3 point change. The proportion of subjects with those levels of change from baseline during each DB treatment period will be summarized by treatment group and time point for the FAS1 and FAS2. The corresponding p-values from Fisher's exact test will be computed for the comparison between treatment groups for each category.

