The change from baseline to 24 hours for each subscale score, each global item score, the total score, and the total raw score will also be analyzed using the Wilcoxon signed-rank test. Baseline scores for each subscale score, each global item score, the total score, and the total raw score will be summarized by treatment group, and will be

compared to 24 hours postdose scores for the DFN-15 group only. The corresponding p-value from the Wilcoxon rank-sum test will be computed for these comparisons.

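### SAP 8.2.14 and 8.2.15 order an independent-samples rank-sum test, beside the correct signed-rank test, for paired baseline-versus-postdose scores within the DFN-15 arm, with no rule for which p-value counts

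*SAP*

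**What the plan says.** Comparing DFN-15 satisfaction with baseline is part of a listed secondary endpoint. SAP 4.2 has "DFN-15 will also be compared to same question in the Baseline PPMQ-R", and Protocol 10.4.2 says the same. The protocol names no test: its Section 10.5.2 leaves secondary analyses to the SAP, and Section 10.1 lets the SAP prevail where the two differ.

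SAP 8.2.14 gives three instructions for this within-arm contrast:

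- The 2- and 4-hour scores and the baseline response "will be compared for the DFN-15 group only. The corresponding p-value from the Wilcoxon rank-sum test will be computed for this comparison".
- In the next paragraph: "P-values from the Wilcoxon rank-sum test will be computed for the comparison between overall treatment satisfaction score at 2 and 4 hours postdose", again against baseline and again for DFN-15 only.
- Then: "P-values from the Wilcoxon signed-rank test will be computed for the difference between baseline PPMQ-R and post baseline for DFN-15 group only".

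SAP 8.2.15 treats the 24-hour PPMQ-R in the same way. For the change from baseline, each subscale, each global item, "the total score, and the total raw score will also be analyzed using the Wilcoxon signed-rank test", with no arm named. Baseline is then compared with 24 hours in the DFN-15 group only, and "The corresponding p-value from the Wilcoxon rank-sum test will be computed for these comparisons".

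The baseline score comes from the subjects who later give the postdose score. Protocol Table 9-2, footnote 3, reads "Treatment satisfaction baseline for the migraine medication to be collected before randomization in the PPMQ-R", and Protocol 9.2.1.2 lists the questionnaire at Visit 2.

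**The concern.** The Wilcoxon rank-sum test assumes two independent samples. A comparison confined to one arm, with each subject measured before and after, has only one sample of pairs. The rank-sum null variance ignores the within-subject correlation, so its p-value is miscalibrated unless that correlation is zero.

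The signed-rank test ordered alongside is the right one. Each contrast therefore gets two p-values, and the SAP does not say which is reported or what happens if they fall on opposite sides of 0.05. Read literally, the paragraph of 8.2.14 that restates the endpoint carries only the rank-sum test. The choice would then be open after unblinding.

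**Working it through.** **The SAP's own pattern.** For functional disability, SAP 8.2.7 uses rank-sum between groups, and within groups "P-values from the Wilcoxon signed-rank test will be computed for the change from baseline within each treatment group". Sections 8.2.14 and 8.2.15 follow that rule for DFN-15 versus placebo but add rank-sum to the within-arm contrast. No reason is given.

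**Number of contrasts.** In 8.2.14: 2 time points x 2 periods = 4. In 8.2.15, with the cost subscale dropped: 4 subscales + 3 global items + total + total raw = 9 scores, x 2 periods = 18. Together 4 + 18 = 22, if both periods are tested.

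**Inputs.** The plan states no figure for these contrasts, so there is none to reproduce. Two-sided alpha of 0.05 is from SAP 6.1.1. The illustrative number of pairs is 600/2 x (1 - 0.15) = 255, from SAP 3.5. (As a check on that reading of dropout, 255 per arm gives 87.4% power for the first co-primary endpoint by the normal approximation, against 88% stated.) A smaller case of 200 pairs allows for the exclusions in SAP 8.2; that number is assumed. The correlation rho and the shift are also assumed.

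**True size of the rank-sum test.** With paired data the variance of the rank difference is about (1 - rho) times what the test uses, so

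size = 2 x (1 - Phi(1.96 / sqrt(1 - rho))).

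At rho = 0.3: 1.96 / sqrt(0.7) = 2.343, giving 1.9%. At rho = -0.2: 1.96 / sqrt(1.2) = 1.789, giving 7.4%.

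**Simulation.** Correlated normal pairs were cut into 7 equally likely categories, with 10,000 runs per null cell and 4,000 at a 0.2 SD shift. Disagreement means that exactly one test rejects at 0.05.

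| rho | Size, formula | Size, simulated (n=255) | Rejection at 0.2 SD, rank-sum vs signed-rank (n=255) | Disagreement (n=255) | Rejection at 0.2 SD (n=200) | Disagreement (n=200) |
|---|---|---|---|---|---|---|
| -0.2 | 7.4% | 7.1% | - | - | - | - |
| 0 | 5.0% | 5.3% | - | - | - | - |
| 0.2 | 2.8% | 2.6% | 58% vs 66% | 8% | 48% vs 55% | 8% |
| 0.3 | 1.9% | 1.9% | 58% vs 70% | 12% | 47% vs 60% | 13% |
| 0.5 | 0.6% | 0.7% | 60% vs 82% | 22% | 47% vs 73% | 26% |

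The signed-rank test held 4.6% to 5.1% in every null cell. A separate run (2,000 per cell, n=255) extended the range. At rho = -0.3 the rank-sum size was 8.9% and the tests disagreed in 10.5% of trials at 0.2 SD. At rho = 0.7 the size was 0.05%, rejection at 0.2 SD was 63% against 95%, and disagreement was 33%.

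**Dependence on the shift.** Disagreement with n=255, 1,500 runs per cell:

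| Shift | rho 0.2 | rho 0.3 | rho 0.5 |
|---|---|---|---|
| 0 | 2% | 2% | 4% |
| 0.1 SD | 6% | 9% | 20% |
| 0.2 SD | 7% | 12% | 21% |
| 0.3 SD | 2% | 3% | 3% |
| 0.4 SD | <0.5% | <0.5% | <0.5% |

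**The case against.** The strongest case is about weight. The valid test is already planned. The contrast is uncontrolled and within one arm. The SAP sets no hierarchy or success rule for secondary endpoints, so nothing in the documents turns on either p-value. If the correlation is positive, the rank-sum test still keeps type I error below 5%: it is inefficient rather than misleading. Disagreement is largest near a 0.2 SD shift and almost vanishes at 0.4 SD. The simulation also models a single 7-category item with a DB1 sample size. That does not represent the 12 contrasts on multi-item scores (4 subscales, total and total raw, x 2 periods) or the unknown number of subjects in DB2.

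Much of this stands, and it limits the consequence. The figures illustrate the problem and do not predict results. The second rank-sum order in 8.2.14 repeats the first and adds no further analysis. In 8.2.15 the two tests overlap only on the DFN-15 arm, because the signed-rank sentence names none.

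It does not remove the defect. The documents do not settle the sign of the correlation, since baseline rates the subject's usual medication and postdose rates study drug. A conservative p-value is still not a 5% test. And nothing in the SAP decides between two p-values for a listed secondary endpoint, although Protocol Section 10 plans hypothesis tests for all secondary efficacy endpoints.

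**Conclusion.** The concern holds. The rank-sum test is the wrong test for the within-DFN-15 baseline-versus-postdose contrasts, and the SAP gives no precedence between it and the signed-rank test. Depending on a correlation the documents do not supply, its true size at nominal 5% could lie anywhere from about 9% (rho = -0.3) to well under 1% (rho of 0.5 or more). Disagreement with the valid test ranges from negligible to roughly a quarter of trials for correlations of 0.2 to 0.5, and to a third at 0.7. These figures assume a 7-category score, 200 to 255 pairs and shifts of 0 to 0.4 SD.

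The effect is confined to within-arm secondary comparisons. The trial loses no power, because the valid test will be run. The correction should be made, but the trial's main conclusions do not depend on it.

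**What to change.** In SAP 8.2.14, delete both rank-sum instructions for the DFN-15 baseline-versus-postdose comparison and attach the planned signed-rank test to it, using subjects with both values. In SAP 8.2.15, delete the rank-sum sentence for baseline versus 24 hours. Reword the sentence before it so that the comparison is not left without a test, and state the arm or arms to which the signed-rank test applies. Keep rank-sum for DFN-15 versus placebo in both sections.

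The cost is three deleted sentences, a small rewording and the removal of redundant output. No new data, method or sample size is needed.

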#### **9.2.1.4.1 Efficacy Assessments**

Subjects will be provided with an eDiary at screening (V1) to collect at least 1 migraine attack during the screening period. The migraine episode may be treated with medication the subject currently uses for a migraine during this period, unless otherwise instructed by the Investigator. After at least 1 migraine attack has been recorded in the eDiary, as instructed, the subject will contact the study site to schedule Visit 2 (V2). At V2 (randomization), it will be determined if subjects meet all study requirements and are eligible to continue in the study. If a subject does not meet all requirements, they must return all study equipment that was provided at the Screening Visit. If randomized, subjects will continue to collect migraine data (for a migraine attack treated with study drug), study drug, last food intake and fat content, and any rescue medication used to treat a migraine. Subjects will record migraine predose assessments, study drug date and time taken, and postdose efficacy data in real time in the 2 DB periods through V4/ET:

- Level of headache pain at predose and at various time points postdose (Levels: 0 = none; 1 = mild; 2 = moderate; 3 = severe)
- Time to meaningful pain relief (based on subject's perception) and time to pain-freedom after study drug
- Migraine symptoms and MBS other than pain: nausea, photophobia, and phonophobia at predose and at various time points postdose; allodynia
- Functional disability at predose and at various time points postdose; scale: 0 = no disability, able to function normally; 1 = performance of daily activities mildly impaired, can still do everything but with difficulty; 2 = performance of daily activities moderately impaired, unable to do some things; 3 = performance of daily activities severely impaired, cannot do all or most things, bed rest may be necessary
- Treatment satisfaction (7-point scale)
- PPMQ-R

MBS will also be collected during Screening via Migraine History evaluation and this Screening MBS will be used for the evaluation of the second co-primary endpoint.

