- The proportion of subjects who have sustained pain freedom at 2 to 24 hours postdose (i.e., pain-free at 2 hours postdose, with no use of rescue medication, and no recurrence of headache pain within 2 to 24 hours postdose) compared between DFN-15 and placebo in each DB period.
- The proportion of subjects who use rescue medication after 2 hours (2 to 24 hours) postdose compared between DFN-15 and placebo in each DB period.
- Treatment satisfaction at 2 hours and 4 hours postdose as determined on a 7-point scale compared between DFN-15 and placebo in each DB period. DFN-15 will also be compared to the same question in the baseline PPMQ-R.
- Treatment satisfaction as measured by PPMQ-R at 24 hours postdose compared between DFN-15 and placebo in each DB period.

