## 6. GENERAL ASPECTS FOR STATISTICAL ANALYSIS

### 6.1. GENERAL METHODS

#### 6.1.1. Summary Statistics

In general, descriptive statistical methods will be used to summarize the data from this study. With appropriate sample sizes, hypothesis testing can be performed for the co-primary and secondary efficacy endpoints.

The term “treatment group” refers to the applied treatment regimen during DB1 or DB2 (DFN-15 120 mg or placebo). All data collected during the study will be included in subject data listings. All subjects entered into the database will be included in subject data listings. Unless otherwise noted, the data will be sorted first by treatment group, subject number, and then by date within each subject number.

Unless stated otherwise, the term “descriptive statistics” refers to number of subjects (n), mean, median, standard deviation, minimum, and maximum for continuous data and frequencies and percentages for categorical data.

All categorical/qualitative data will be presented using absolute frequency counts and percentages. The total number of subjects in the treatment group overall (N) in the specified population will be used as the denominator for percentage calculations, unless stated otherwise in the table shell. All percentages will be presented in parentheses with 1 decimal point, unless otherwise specified. Percentages equal to 100 will be presented as 100% and percentages will not be presented for zero frequencies.

Unless specified otherwise, all statistical testing and confidence intervals (CIs) will be 2-sided and will be performed using a significance (alpha) level of 0.05.

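### The satisfaction comparisons with baseline PPMQ-R are tested in the DFN-15 group only, so their p-values cannot separate a drug effect from a shift that both arms share

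*SAP*

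**What the plan says.** Protocol 10.4.2 lists satisfaction at 2 and 4 hours as a secondary endpoint compared with placebo, and adds: "DFN-15 will also be compared to the same question in the baseline PPMQ-R". Footnote 3 of Protocol Table 9-2 fixes the timing: "Treatment satisfaction baseline for the migraine medication to be collected before randomization in the PPMQ-R". Protocol 9.2.1.2 lists the baseline questionnaire among the Visit 2 procedures without limiting it to an arm.

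SAP 8.2.14 contains three kinds of analysis of the 2- and 4-hour score:

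- Between arms, on the postdose score: "The corresponding p-values from the Wilcoxon rank-sum test will be computed for the comparison between treatment groups". Fisher's exact tests on collapsed categories follow later in the section.
- Descriptive, both arms: the difference between the postdose score and "the baseline PPMQ-R response for the same question will be summarized by treatment group for the FAS1 and FAS2".
- Against baseline, one arm: rank-sum p-values for DFN-15 only, and "P-values from the Wilcoxon signed-rank test will be computed for the difference between baseline PPMQ-R and post baseline for DFN-15 group only".

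SAP 8.2.15 compares the 24-hour PPMQ-R scores between arms by rank-sum. It then has the baseline scores "compared to 24 hours postdose scores for the DFN-15 group only", again by rank-sum. A separate sentence there orders a signed-rank test of the change to 24 hours and names no arm. Under SAP 6.1.1, tests "will be 2-sided and will be performed using a significance (alpha) level of 0.05". The SAP labels its subgroup analyses and those in section 8.3 exploratory, but not these.

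**The concern.** The two ratings being compared are not of the same thing. The baseline appears to rate the subject's usual migraine medication. That is an inference: Table 9-2 says only that it concerns the migraine medication, but Protocol 9.2.1.4.1 says of the screening attack, "The migraine episode may be treated with medication the subject currently uses for a migraine during this period". The postdose score rates one attack treated with blinded study drug. Setting and expectation differ as well. In DB2 the pain level can also differ, because attacks may be treated at any level while inclusion criterion 5 requires usual untreated pain to be moderate or severe.

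Any of these can move satisfaction in both arms without a drug effect. A change tested in one arm keeps the whole of such a shift, whereas a comparison with placebo cancels it. At stake is the meaning of a p-value attached to part of a protocol secondary endpoint: it can be small for an inert product. The data that would control for this are already collected.

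**Working it through.** **Sample size.** The plan gives no power or variance figure for satisfaction. Its first co-primary calculation fixes a plausible n: 600 × (1 − 0.15) / 2 = 255 per arm. With 17.6% against 29.2%, 255 per arm gives 87.4% power by the pooled-variance normal approximation, close to the stated 88%.

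**Assumptions not in the documents.** Scores are normal with mean 3.5 and SD 1.6, rounded and limited to 1–7. The correlation r between baseline and postdose is 0.2 or 0.5. There is no drug effect, and the same shift towards satisfied applies in both arms. A second setting has a subject effect of SD 1 plus an error of SD 1 on each occasion, so the SD of change is √2 ≈ 1.41.

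**Hand check at a 0.25-point shift.** Approximate rejection rate of a paired test = Φ(shift × √n / SD of change − 1.96), with √255 = 15.97 and 0.25 × 15.97 = 3.99.

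- SD 1.6, r = 0.2: SD of change = 1.6 × √(2 × 0.8) = 2.02. Then 3.99 / 2.02 − 1.96 = 0.01, giving about 51%.
- SD 1.6, r = 0.5: SD of change = 1.6 × √(2 × 0.5) = 1.60. Then 3.99 / 1.60 − 1.96 = 0.53, giving about 70%.
- Second setting: 3.99 / 1.41 − 1.96 = 0.87, giving about 81%.

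Simulation of the signed-rank test gives 48%, 66% and 77%, slightly lower, as expected with ties and a bounded scale.

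**Simulation over a range of shifts** (SD 1.6, 2,000 runs per setting). Rejection by the DFN-15-only signed-rank test:

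| Common shift | r = 0.2 | r = 0.5 |
|---|---|---|
| 0 | 4% | 4% |
| 0.1 | 13% | 15% |
| 0.2 | 33% | 47% |
| 0.3 | 63% | 81% |
| 0.5 | 96% | 99.7% |
| 0.3 towards dissatisfied | 63% | 81% |

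At 0.3 towards satisfied, every rejection is in the direction of benefit. At 0.3 the other way, every one is in the direction of harm. The DFN-15-only rank-sum test against baseline shares the problem, with 53% to 54% rejection at a 0.3-point shift towards satisfied. Across all these settings the planned between-arm rank-sum test of the postdose score rejects in 4.3% to 5.9% of runs.

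**Which between-arm test uses the baseline best.** For score variance σ², the relevant variance is σ² for the postdose score, 2σ²(1 − r) for the change, and about σ²(1 − r²) after adjustment for baseline. At r = 0.2 these are 1.00, 1.60 and 0.96 times σ². At r = 0.5 they are 1.00, 1.00 and 0.75 times σ². Simulated power for an assumed true effect of 0.4 points agrees:

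- planned postdose rank-sum: 77–78%
- rank-sum on the change: 54–72%
- rank ANCOVA on baseline: 79–86%, with type I error near 5%

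**The case against.** The strongest reply is that the randomized comparison is already planned. SAP 8.2.14 and 8.2.15 test the postdose scores between arms. Baseline precedes randomization, so in DB1 its expected value is equal in the two arms, and the difference in postdose score estimates the same effect as the difference in change. The 2- and 4-hour change is also displayed for both arms, so a reader can see the placebo shift. This stands. It does not rescue the separate p-values against baseline, which no placebo figure enters.

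A second reply is that Protocol 10.4.2 asks how DFN-15 compares with the medication rated at baseline, which a comparison with placebo does not answer. That also stands. No analysis of these data isolates that contrast, which is why it belongs in a descriptive display.

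Three stronger readings are tempting, and the documents do not support them:

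- A reader might infer that any shift will be reported as a drug benefit. Neither document says how the within-arm p-value will be interpreted. A shift towards dissatisfaction would count against the drug, and SAP 8.1.1 rests trial success on the co-primary endpoints alone.
- A reader might take the 24-hour signed-rank test to be confined to DFN-15. The sentence in SAP 8.2.15 names no arm; the restriction attaches to the rank-sum comparison.
- A reader might assume regression to the mean among dissatisfied volunteers. No inclusion criterion selects on satisfaction, so this is possible but not established.

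**Conclusion.** The point holds for the DFN-15-only p-values: rank-sum and signed-rank at 2 and 4 hours, and rank-sum at 24 hours. They cannot separate a drug effect from a shift common to both arms, in either direction. With 255 per arm and no drug effect, a 0.25-point common shift makes the signed-rank test significant in about 48% to 77% of trials. That range rests on an assumed scale distribution, SD, correlation and shift, none of which the documents give.

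The planned between-arm tests are valid against such a shift. Their limitation is that they leave the baseline score unused, which costs some precision. The co-primary analyses do not depend on any of this. It is a minor improvement to one group of secondary analyses.

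**What to change.** In SAP 8.2.14, for DB1 and DB2, make the inferential comparison a between-arm rank ANCOVA of the 2- and 4-hour score adjusted for the baseline PPMQ-R item. Do not use a rank-sum test on the change, which can lose power. Replace the DFN-15-only p-values with the change from baseline, as an estimate and CI for DFN-15 beside the same figure for placebo, labelled descriptive.

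Apply the same to the 24-hour PPMQ-R scores in SAP 8.2.15, and reword the signed-rank sentence that names no arm. Name the Visit 2 questionnaire as the covariate in both periods. Otherwise the general definition in SAP 6.2.1, the latest measurement before each period's dose, could be read as the DB1 24-hour score when DB2 is analysed.

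The cost is SAP wording and limited reprogramming; no new data are needed. There are two downsides. Subjects without a baseline PPMQ-R drop out of the adjusted analysis. And the tested result is DFN-15 against placebo, so the comparison with the baseline medication that Protocol 10.4.2 names remains descriptive; that should be recorded in SAP section 11 as a change from the protocol.
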